5.1.2 Blinding, Packaging, and Labeling of Study Drug

This is a randomized and unblinded study, consequently no effort is required to blind study drug or active comparator from any of the study personnel at the clinical site. A pharmacist will be responsible for the compounding of individual doses of study drug (SelK2) for patients randomized to receive SelK2.

Each SelK2 vial is labeled in accordance with specific country regulatory requirements as well as with the study number, specific drug contents, and unique vial number.

Enoxaparin pre-filled syringes will be labeled in accordance with specific country regulatory requirements.

5.1.3 Randomization Methods and Procedures

Patients will be screened prior to randomization and assigned a Subject ID number by IRT. After patient's eligibility is confirmed, treatment assignment will be determined by a validated central randomization schedule using IRT (Interactive Response Technology). If a patient meets all of the inclusion criteria and none of the exclusion criteria, delegated and approved site personnel, trained on the use of the IRT, will randomize the patient. The IRT system will assign the patient a treatment group based on the next available slot in the randomization scheme. It is important to note that the randomization web entry should **only** be made after eligibility has been established. Prior to randomization, baseline efficacy and safety assessments will be taken.

Patients will be randomly placed into one of two treatment arms:

- 1) 7.5 mg/kg SelK2, IV or
- 2) 40 mg enoxaparin, SC, QD.

Patients will be randomized to these two treatment arms in a 1:1 ratio. Randomization will be stratified by site.

For patients randomized into the 7.5 mg/kg SelK2 arm, the IRT system will calculate the number of vials required based on the patient weight and will provide the user the appropriate vial numbers to use.

Changes in Randomization Procedure when Adaptive arm is activated and enrollment into the SelK2 only arm is discontinued:

When the adaptive arm is activated and the SelK2 only arm is closed, the central randomization process will allow for placing patients randomly into one of the below two treatment arms and randomization will continue to be stratified by site.

Patients will be randomly placed into one of two treatment arms:

- 1) 40 mg enoxaparin, SC, QD, or
- 2) 7.5 mg/kg SelK2, IV and 40 mg enoxaparin, SC, QD.

The randomization ratio will be altered to a 2:1 ratio (2 patients receiving 7.5 mg/kg SelK2 and enoxaparin to every 1 patient receiving Enoxaparin only) so that the total number of patients in each of the two remaining arms will be approximately equivalent at the end of the study. This modified randomization ratio will be controlled by the centralized IRT system.

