3.2 Number of Patients

Approximately 190 patients are planned to be enrolled in this clinical study as designed. Based on adaptive design, if a third cohort of the study is added, an additional 95 patients may be added for a maximum of approximately 285 patients enrolled.

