10.0 STATISTICAL METHODS AND PLANNED ANALYSES

10.1 Sample Size and Power

Assuming that the rate of VTE for the active comparator (enoxaparin) arm of this study will be 25%, it is estimated that a sample size of 76 evaluable patients per arm should give the study 80% power of declaring non-inferiority between the SelK2 arm and the enoxaparin active comparator arm. This calculation uses a one-sided 90% CI with a non-inferiority margin of 15%. This calculation assumes that the underlying rate of VTE for the SelK2 and enoxaparin arms will be identical at 25% and with the non-inferiority margin set as at the midpoint between the expected active therapy response compared to an assumed placebo event rate in this patient population of 55%. Consequently, making the conservative estimate that up to 20% of randomized patients may not yield evaluable endpoint data, a total of 95 patients will be enrolled per arm to provide at least 76 endpoint evaluable patients per arm.

Sample Size Considerations for Adaptive Arm:

With the same assumptions as above the for active comparator (enoxaparin) arm of the study event rate, it is estimated that a sample size of 76 evaluable patients in a combination therapy arm of SelK2 and enoxaparin should give the study 80% power of declaring superiority between the SelK2 and enoxaparin arm and the enoxaparin active comparator arm for an estimated SelK2 and enoxaparin VTE event rate of 6% (an 19% difference between combination treatment effect and active comparator treatment effect). This calculation assumes a two-sided 0.1 alpha, a Pearson Chi-squared test, and a superiority comparison.

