10.5 Steering and Safety Committee Data Reviews and Interim Analyses

A formal study Steering and Safety Committee will consist of at least 3 clinicians (with experience and expertise in venous thrombosis). The Steering and Safety Committee will be charged with reviewing in an unblinded fashion all accumulating safety and efficacy data to assure overall patient safety in this study.

The following efficacy and safety data will be provided to the Steering and Safety Committee by treatment group, and where appropriate by study visit day and time:

- Overall VTE event rate (as adjudicated);
- Individual component event rate (individual components of the composite VTE event rate);
- Incidence of bleeding events (as adjudicated) including the following will be tabulated by treatment:
 - 1) Major Bleeding event (MB),
 - 2) Clinically Relevant Non-Major Bleeding event (CRNMB),
 - 3) Minor Bleeding even, or
 - 4) Combination of MB and CRNMB
- Incidence of AEs (including SAEs) ;
- Clinical laboratory values (hematology, serum chemistries, urinalysis, and coagulation parameters);
- ECGs; and
- Vital signs.

The Steering and Safety Committee will use all of the above accumulating data to assess the safety of continuing each aspect of this study.

Interim Analyses to support decision on whether or not to recommend activation of Adaptive Arm:

The Steering and Safety Committee is also charged with making recommendations to the Sponsor with regards to the activation of the adaptive arm that investigates the efficacy and safety of SelK2 use in combination with enoxaparin. At certain enrollment milestones, the Steering and Safety Committee will be presented with interim analysis tables which will include VTE event rates by treatment group with 80% confidence intervals and the calculated risk difference (the difference

between the cumulative incidence in the SelK2 arm to that of the cumulative incidence the enoxaparin arm) with 80% confidence intervals. The conditional powers for demonstrating non-inferiority at the end of the trial based upon accumulated data at interim may also be computed. These interim analyses will be part of the data set used by the Committee as they determine whether or not to recommend activation of adaptive arm. This adaptive arm may be initiated if the Steering and Safety Committee determines that preliminary data suggests the potential for an additive effect in VTE reduction and that the combination does not pose an additional safety risk.

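### Activating the adaptive arm closes the SelK2-only arm, yet the sample-size figures still describe three full arms of 95 and do not say that the 80% non-inferiority power lapses

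*Combined protocol and SAP*

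**What the plan says.** Section 5.1.3 starts with two arms: "Patients will be randomized to these two treatment arms in a 1:1 ratio". It then describes the change that applies "When the adaptive arm is activated and the SelK2 only arm is closed". From that point, allocation is two combination patients to one enoxaparin patient, "so that the total number of patients in each of the two remaining arms will be approximately equivalent at the end of the study".

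The current text does not say when the switch falls. Section 10.5 says only "At certain enrollment milestones". A percentage range for activation appears in the list of protocol modifications, but as replaced text, so it cannot fill the gap. Nothing states what stops enrolment after the switch.

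On size, Section 3.2 plans about 190 patients and says that "an additional 95 patients may be added for a maximum of approximately 285 patients enrolled". The synopsis also gives 285 as an upper limit. Section 4.0 describes 95 in each of the two initial arms plus an added arm of 95.

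On power, Section 10.1 says "it is estimated that a sample size of 76 evaluable patients per arm should give the study 80% power" for non-inferiority of SelK2 to enoxaparin, with 25% VTE in both arms, a margin of 15 points and a one-sided 90% confidence limit. The synopsis repeats this. Section 10.3.3 keeps SelK2-only against enoxaparin among the planned comparisons, with the 15% criterion.

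**The concern.** The size and power statements fit a design in which all three arms fill to 95. The amended design stops SelK2-only wherever it stands at activation. Three things are then left loose: the number of patients to expect, whether 2:1 serves its stated purpose, and the power of a non-inferiority test that is still planned but may have far fewer SelK2-only patients than Section 10.1 assumes. The third matters most. Failure to show non-inferiority in a truncated arm could be read as evidence against SelK2 monotherapy by someone who believes the comparison had 80% power.

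**Working it through.** **Inputs.** Target of 95 per arm and 190 in the two initial arms (Sections 3.1, 4.0); 1:1 before and 2:1 after the switch (5.1.3); 25% VTE in both arms, margin 0.15, one-sided alpha 0.10, 20% not evaluable (10.1); combination rate 6% and two-sided alpha 0.10 for superiority (10.1). The switch point is not given, so I show one third, half and two thirds of 190. Let e be the number of patients per initial arm at the switch.

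**1. The plan's own figures.** n per arm = 2 × 0.25 × 0.75 × (1.2816 + 0.8416)² / 0.15² = 75.13, so 76. Then 76 / 0.8 = 95, 2 × 95 = 190 and 3 × 95 = 285. The stated figures reproduce, with 285 as three full arms.

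**2. Total after closure.** With 95 in each open arm, total = 190 + e. Reaching 285 on these targets would need e = 95, when enoxaparin is already full too.

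**3. Ratio.** If m further enoxaparin patients enter at 2:1, combination has 2m and enoxaparin e + m. These are equal only if m = e, so post-switch enrolment (3m) must be 1.5 times pre-switch enrolment (2e). With 95 per open arm, e = 47.5: a switch at 95 randomized, half of 190. For other switch points, ending at 95 and 95 needs 95:(95 − e).

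If 2:1 is kept and enrolment stops when combination reaches 95 (my assumption), enoxaparin ends at e + 47.5.

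| Switch (share of 190) | e | Total, 95 per open arm | Ratio needed | Enoxaparin if 2:1 is kept |
|---|---|---|---|---|
| 1/3 | 31.7 | 222 | 1.5:1 | 79 |
| 1/2 | 47.5 | 238 | 2:1 | 95 |
| 2/3 | 63.3 | 253 | 3:1 | 111 |

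**4. Effect on superiority power.** Power = Φ{[0.19 − 1.645 √(p̄(1 − p̄)(1/n₁ + 1/n₂))] / √(0.1875/n₁ + 0.0564/n₂)}, where p̄ is the pooled rate. With 76 evaluable in each arm it is about 95%. With about 63 enoxaparin (0.8 × 79) and 76 combination it is about 93%. (The plan states 80% for this comparison; that difference is a separate matter, and only the change is used here.)

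**5. Non-inferiority power.** Power = Φ(0.15/SE − 1.2816), with SE² = 0.1875/n(SelK2) + 0.1875/n(enoxaparin).

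- As planned, 76 and 76: SE = 0.0702, power 80.3%.
- Half-way switch, 0.8 × 47.5 = 38 SelK2-only. Against 38 concurrent enoxaparin patients, SE = 0.0993, power 59.0%. Against all 76 enoxaparin patients, SE = 0.0860, power 67.8%.
- Switch at one third, about 25 SelK2-only: about 48% against concurrent controls.

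**The case against.** Much of the opposing case stands, and it limits how far the point goes.

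A reader might infer that 2:1 works only for a switch at exactly half of enrolment. The documents do not support that. Section 5.1.3 promises approximate equality, and half is right only for the planned 190 with 95 per open arm. Measured on the enrolment finally reached, the balancing switch is at 40% (2e of 5e). If combination stops at 95, a switch between about 42% and 60% of 190 leaves enoxaparin at 87.5 to 104.5, within about 10%.

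A reader might also infer that 285 is contradicted. It is worded as a maximum, and lower totals respect it. Equal open arms can even reach it: 57 SelK2-only, 114 enoxaparin and 114 combination sum to 285, though not with arms of 95.

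The strongest reading is that equal arms, the maximum and 80% power cannot all hold. That goes too far as a charge of contradiction. Equal arms and the maximum do hold together: 95 and 95 in a total of 238. Section 10.1 ties the 80% to 76 evaluable per arm and does not expressly claim it after closure; it gives a separate calculation for the combination comparison. The removal of the SelK2-only arm is openly stated.

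Finally, 59% and 68% are unconditional figures at 25% in both arms. Closure would follow unblinded review of interim VTE rates, so they are not the power of an arm closed because of its data.

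What remains is an omission with consequences: the non-inferiority test survives activation in Section 10.3.3, and no passage says that its stated power does not.

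**Conclusion.** The point holds in a limited form. After activation, 285 is a loose ceiling that matches three full arms; with 95 per open arm the trial would enrol about 222 to 253 patients for a switch between one third and two thirds of 190. The 2:1 ratio meets its purpose only around one unstated switch point, but the cost in superiority power is small, about 93% against 95% for a switch at one third. The substantive part is non-inferiority: 80% falls to about 59% (concurrent controls) or 68% (all enoxaparin) at a half-way switch, and lower for an earlier one. The 68% figure counts enoxaparin patients randomized after SelK2-only closed; the plan does not say which enoxaparin patients the comparison uses. All figures rest on the plan's rates and 20% non-evaluable share, and the totals on stopping both open arms at 95. This should be corrected; it does not invalidate the design.

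**What to change.** - **Section 5.1.3 and the IRT:** set the post-switch ratio from the counts at the switch, combination to enoxaparin as 95:(95 minus enoxaparin patients already randomized), and state that enrolment stops at 95 in each open arm. A rounded ratio is enough, since the aim is approximate equality. The timing of activation can stay with the committee and the sponsor.
- **Synopsis, Sections 3.2 and 4.0:** give the expected total after activation as 190 plus the SelK2-only patients at closure, about 238 for a half-way switch.
- **Synopsis and Section 10.1:** state that the 80% non-inferiority power applies only if the adaptive arm is not activated, and give the reduced figures with their assumptions, including which enoxaparin patients serve as controls.

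The cost is wording, one IRT setting and a less favourable power statement. No patients beyond the stated maximum are needed. A late switch makes the ratio steeper (3:1 at two thirds) and leaves fewer concurrent enoxaparin controls for the combination arm, about 32 randomized in that case.

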5.1.4 Supply, Storage, Accountability, and Disposition of Study Drug

The pharmacist will inventory and acknowledge receipt of all shipments of study drug. All study drug must be kept in a locked area with access restricted to designated study personnel. The study drug must be stored in accordance with the package instructions. All storage records (i.e. temperature logs) must be maintained. The pharmacist will also keep accurate records of the quantities of study drug dispensed and used by each patient. A monitor will ensure accountability of all study drug used. Refer to the Pharmacy Manual for further detailed instruction on study drug (both SelK2 and enoxaparin) storage and accountability.

At the conclusion of the study, after final drug reconciliation is completed by the monitor, all unused study drug can be destroyed at site (with appropriate documentation) or can be returned to a designee as instructed by Sponsor. IQVIA will assure that a final report of drug accountability is prepared and maintained by the Investigator.

Neither SelK2 nor enoxaparin will be provided to study participants after their participation in this study is completed. Neither SelK2 nor enoxaparin will be made available to any participants at the conclusion of this study.

5.2 Dosage Schedule

5.2.1 Dosing of SelK2

For those randomized to receive SelK2, patients will receive a single dose of 7.5 mg/kg SelK2 via IV administration at least 12 hours prior to but not longer than 24 hours prior to the start of the TKA surgery. SelK2 will be given as an approximately 100 mL IV infusion over approximately 30 minutes (\pm 15 minutes).

5.2.2 Dosing of Enoxaparin

For those randomized to receive enoxaparin, patients will receive 40 mg enoxaparin administered via SC injection 12 hours after TKA surgery followed by daily SC injections of 40 mg enoxaparin through and including Day 11 (\pm 2 days). Daily dosing of enoxaparin should continue until the venogram is completed. At the discretion of the PI, sites also have the option of giving an additional 40 mg enoxaparin SC dose 12 hours PRIOR to TKA surgery.

5.2.3 Adaptive Arm: Dosing of SelK2 and Enoxaparin

When the adaptive arm is activated, for those randomized to receive SelK2 and enoxaparin in combination, patients will receive a single dose of 7.5 mg/kg SelK2 via IV administration at least 12 hours prior to but not longer than 24 hours prior to the start of the TKA surgery. SelK2 will be given as an approximately 100 mL IV infusion over approximately 30 minutes (\pm 15 minutes). Additionally, patients will receive 40 mg enoxaparin administered via SC injection 12 hours after TKA surgery followed by daily SC injections of 40 mg enoxaparin through and including Day 11 (\pm 2 days).

5.3 Prior and Concomitant Medications

In general, medications consistent with the standard care of patients undergoing TKA (e.g., tranexamic acid, etc.) will be allowed during this study.

Except for the protocol prescribed SelK2 or enoxaparin, all efforts should be made to exclude the concomitant use of anticoagulants/antiplatelet agents (e.g., warfarin, dabigatran, rivaroxaban, apixaban, clopidogrel, phenprocoumon, acenocoumarol, edoxaban, prasugrel, ticagrelor, sulodexide, aspirin+dipyridamole, cilostazol, etc.) throughout the duration of the study, from Day 1 through Day 57 UNLESS medically necessary (i.e., patient experiences a VTE, myocardial infarction, etc.). Use of NSAIDs is discouraged and should only be used when unavoidable. NSAIDS should be used in the lowest dose and for the shortest period of time possible. Any concomitant use of aspirin should be avoided (except for low dose aspirin, 100 mg or less).

Any medication or non-pharmacological therapy (in addition to the study drug) that is taken by or administered to the patient at any point during the course of this study must be recorded in the eCRF. The entry must include the dose, regimen, route, indication, and dates of use. The collection of prior medications will include medications used within the past 6 months from the estimated Day 1 date.

Patients may not participate in any other interventional drug study for at least 60 days prior to starting this study (Study Day 1) and may not participate in any other interventional drug study throughout the study period.

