4.2 Exclusion Criteria

Patients presenting with any of the following will not be included in the study:

1. Body weight <50 kg at Screening;
2. Previous deep vein thrombosis (DVT) of the leg or pulmonary embolism (PE) within the past year;
3. Malignancy within 1 year, except for basal or squamous cell carcinoma of the skin or carcinoma *in situ* of the cervix that has been successfully treated;
4. Myocardial infarction, transient ischemic attack or stroke within the last 6 months;
5. Patients at increased risk of bleeding because of history of increased bleeding tendency (i.e., history of bleeding diathesis) or any other condition that in the opinion of the Investigator increases risk of bleeding (e.g., recurrent gastrointestinal ulcer) or patients with a history of intracranial or intraocular bleeding;
6. Brain, spinal, or ophthalmologic surgery within the past 3 months;
7. Cockcroft-Gault calculated creatinine clearance <30 mL/min at Screening (central lab will calculate the Cockcroft-Gault value);
8. Screening laboratory results as follows, or any other clinically significant abnormalities in screening laboratory values that, in the opinion of the PI, would render a patient unsuitable for inclusion:
 - ALT or AST >1.5x ULN
 - Total bilirubin >1.5x ULN

- Platelet count <150,000 or recent (over the last 3 months) history of thrombocytopenia (e.g. platelet count <150,000);

9. Positive test for human immunodeficiency virus (HIV; by history of having HIV antibodies), positive hepatitis B (hepatitis B surface antigen [HBsAg]) or hepatitis C (anti-hepatitis C antibody [Anti-HCV]) at Screening;
10. Uncontrolled hypertension as judged by the Investigator;
11. Clinically significant abnormal ECG at Screening, as judged by the Investigator;
12. Active infection;
13. Unable to undergo venography due to a known allergy to the contrast agent, anticipated poor venous access, impaired renal function, or any other reason identified and specified by the PI;
14. Hypersensitivity to enoxaparin or any contraindication listed in the local labeling of enoxaparin;
15. Any underlying condition (e.g., atrial fibrillation, mechanical heart valve, or recent pulmonary embolism) that may lead to the required concomitant use of anticoagulants/antiplatelet agents (e.g., warfarin, dabigatran, rivaroxaban, apixaban, clopidogrel) that may affect study outcome or any other drug influencing coagulation (except low dose aspirin (100 mg or less));

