10.2 Analysis Populations

Assignment of patients to analysis populations will be done prior to clinical data lock for the study. The following populations will be defined: Intent-to-Treat (ITT), modified Intent-to-Treat (mITT), Per-Protocol (PP), and Safety.

Intent-to-Treat (ITT): All patients who are randomized. The ITT population will be analyzed by randomized treatment group.

Modified Intent-to-Treat (mITT): All patients in the ITT population who also have a successful venogram or symptomatic VTE event which allow for assessment of the primary efficacy outcome.

Per-Protocol (PP): All mITT patients who complete the study and have no major protocol violations that will impact the efficacy assessments.

Safety: All patients who received at least 1 dose of study drug. Safety population will be analyzed by actual treatment received.

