10.3.2.2 Demographics, Background, and Baseline Characteristics

Demographics, background (e.g., medical history), and baseline characteristics will be summarized. Protocol deviations/violations will be provided as a patient data listing only. Major protocol deviations/violations will be identified for analysis purposes.

The demographics and baseline characteristics summary will be presented for the ITT, mITT, PP, and safety populations to allow review of the characteristics of those included in the efficacy and safety analyses, which will be based on these analysis populations. Background (e.g., medical history) summary will be presented for the ITT population only.

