10.3.2.3 Prior and Concomitant Medications

Medications used in this study will be coded by the World Health Organization Drug Dictionary (WHODD), and summarized as frequency tables for the preferred terms in 2 parts:

- Prior medication: any medication that started prior to the first dose of study drug, regardless of when it ended (collected for medications given up to 6 months prior to Day 1).

- Concomitant medication: medication received at or after dosing of study drug, or medication that was received prior to dosing with study drug and continued after dosing of study drug.

If medication start date is on the day of or after the first dose of study drug, then medication will be summarized as concomitant medication regardless of whether the medication end date is missing or not. If the medication end date is before the date of first dosing of study drug, then the medication will be summarized as prior medication regardless of whether the medication start date is missing or not. Note that medication that started prior to first dosing of study drug and continued after dosing will be summarized as prior medication and separately as concomitant medication. Both prior and concomitant medications will be based on the ITT population. For medications with partial start dates, missing month will be imputed with January and missing day will be imputed with 1. For medications with partial stop dates, missing month will be imputed with December and missing day will be imputed with the last day of the month.

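### Section 5.3 exempts aspirin of 100 mg or less by dose alone, so new low-dose aspirin before venography is not clearly barred and no planned table isolates it

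*Combined protocol and SAP*

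**What the plan says.** Section 5.3 has two relevant sentences. The general one says "all efforts should be made to exclude the concomitant use of anticoagulants/antiplatelet agents" from Day 1 through Day 57 unless medically necessary. Its list of examples is open-ended and names aspirin combined with dipyridamole, but not aspirin alone. The specific one says "Any concomitant use of aspirin should be avoided (except for low dose aspirin, 100 mg or less". It sets no start date, indication or requirement of prior use. Section 5.3 also opens by generally allowing medications that are standard for TKA.

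Exclusion 15 in Section 4.2 covers underlying conditions "that may lead to the required concomitant use of anticoagulants/antiplatelet agents" and "any other drug influencing coagulation (except low dose aspirin (100 mg or less". It carries the same dose-only exemption and treats aspirin as a drug that acts on coagulation.

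Sites are unblinded: Section 5.1.2 says "no effort is required to blind study drug or active comparator from any of the study personnel". The primary endpoint is total VTE from randomization to completion of the venogram, and the main analysis uses mITT (Section 10.3.3).

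Section 10.3.2.3 plans frequency tables by preferred term on the ITT population. The second of them counts drugs carried on past dosing as well as new ones, in these words: "Concomitant medication: medication received at or after dosing of study drug, or medication that was received prior to dosing with study drug and continued". Medications are recorded up to Day 57 (Table 1). Per-protocol patients must "have no major protocol violations that will impact the efficacy assessments" (Section 10.2). Section 10.3.2.2 adds "Major protocol deviations/violations will be identified for analysis purposes", but no list of such violations is given.

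**The concern.** A site could reasonably apply the specific aspirin sentence over the general antiplatelet sentence and conclude that a new 100 mg start is allowed. The opportunity differs by arm. Sites know the assignment, enoxaparin patients receive daily injections until venography, and SelK2-only patients are given no study drug after surgery. If new aspirin were concentrated in the SelK2-only arm and lowered VTE, that arm's rate would fall for a reason other than SelK2, and the difference would move toward non-inferiority. Blinded adjudication protects the classification of outcomes but does not prevent unequal co-medication.

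The planned outputs would not settle the question. Aspirin would appear as a preferred term, so a large excess in one arm might be noticed. The table could not say whether that use was new, whether it began before venography, or whether it was in the analyzed patients. Subtracting the prior-medication table does not help, because that table also counts drugs stopped before dosing.

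**Working it through.** **Inputs from Section 10.1.** 76 evaluable patients per arm, 25% VTE in both arms, margin 15 points, one-sided 90% CI, 80% power, 20% non-evaluable, assumed placebo rate 55%.

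**The plan's own figure.** n = (1.2816 + 0.8416)² × 2 × 0.25 × 0.75 / 0.15² = 75.1, so 76 per arm. Power at 76 is 80.3%, and 76 / 0.80 = 95. The plan's numbers reproduce.

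**Assumptions not in the documents.** A share s of the SelK2-only arm newly starts aspirin, which lowers VTE risk in those patients by a fraction r (10%, 30% or 50%). Except where stated, nobody in the enoxaparin arm does so.

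**Formulas.** pS = true SelK2 rate × (1 − s × r), and pE = 0.25. SE = √[pS(1 − pS)/76 + pE(1 − pE)/76]. The probability of declaring non-inferiority is Φ((0.15 − (pS − pE))/SE − 1.2816).

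**True SelK2 rate at the margin (40%).**
- No aspirin: SE = √[(0.24 + 0.1875)/76] = 0.0750, and Φ(0 − 1.2816) = 10.0%.
- Example with s = 10%, r = 50%: pS = 0.40 × 0.95 = 0.38, SE = 0.0746, and Φ(0.02/0.0746 − 1.2816) = 15.5%.

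| Share (patients of 76) | r = 10% | r = 30% | r = 50% |
|---|---|---|---|
| 5% (about 4) | 10.5% | 11.5% | 12.6% |
| 10% (about 8) | 11.0% | 13.1% | 15.5% |
| 20% (about 15) | 12.0% | 16.9% | 22.9% |

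Exact binomial enumeration with the same Wald limit agrees to within 0.3 points (9.9% with no aspirin, 23.2% in the last cell). The rate reaches 15% when s × r = 4.57%, which is 76 × 0.40 × 0.0457 = 1.4 fewer events. With 20% use in the SelK2 arm and 10% in the enoxaparin arm it is 11.4-18.2%. With 20% in both it is 10.7-14.1%.

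**True SelK2 rate further from the margin.**
- At 45%: 2.6% with no aspirin, at most 8.9% (s = 20%, r = 50%).
- At 55%, the assumed placebo rate: 0.05% with no aspirin, at most 0.6%.

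**Would removing starters from PP correct it?** Take a true arm average of 40%, and let q be the starters' underlying rate. The remaining rate is (0.40 − s × q)/(1 − s), with 68 or 61 SelK2 patients left. If q = 40%, PP error returns to 10%. If starters are at higher risk, removal biases the comparison:

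| s, q | Remaining rate | PP after removal | Left in, r = 10% | Left in, r = 30% | Left in, r = 50% |
|---|---|---|---|---|---|
| 10%, 50% | 38.9% | 12.8% | 11.2% | 14.0% | 17.2% |
| 10%, 60% | 37.8% | 16.0% | 11.5% | 14.9% | 19.0% |
| 20%, 50% | 37.5% | 16.7% | 12.6% | 19.0% | 27.3% |
| 20%, 60% | 35.0% | 25.9% | 13.1% | 21.3% | 32.0% |

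Removal is worse than leaving starters in for all four rows if aspirin's effect is 10%, for two of four at 30%, and for none at 50%.

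**The case against.** The strongest reply is that Section 5.3 already covers the case. A site that adds aspirin as extra thromboprophylaxis adds an antiplatelet agent, which the general sentence asks it to avoid unless medically necessary. On that view the low-dose exemption only tolerates background cardioprotective use and matches the eligibility exemption. This is a fair reading, and it is why the text is ambiguous rather than permissive. It does not close the gap, because the specific sentence exempts by dose and a site could follow it in good faith.

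The reply also has force on data and scale. Dose, indication and dates must be recorded, populations are assigned before data lock, and the Synopsis allows further robustness analyses. A split by start date could therefore be made later, and what is missing is a rule and an output, not information. Giving SelK2-only patients no study drug after surgery does not leave them without prophylaxis by design: the single pre-operative antibody dose is the treatment under test, and its PK and PD are followed to Day 57. All of this stands and keeps the priority minor.

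A reader might infer that sites do start aspirin after TKA, or do so more often in the SelK2-only arm. The documents do not say so. A reader might also infer that PP should simply drop starters. Starting aspirin happens after randomization and may track risk, so that removal is not a dependable correction.

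**Conclusion.** The point holds as an ambiguity in a conduct rule together with a planned table that cannot resolve it. With one-arm use of 5-10% and a 10-50% reduction in VTE, false non-inferiority at the margin rises from 10% to about 10.5-15.5%. The larger values at a 20% share need more use than anything in the documents suggests. Share, effect and concentration in one arm are all assumed, and the calculation uses the planned 76 per arm.

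A reader might infer that aspirin could carry an inert drug to a non-inferiority claim. The figures do not support that: the chance is at most 0.6% at a true rate of 55%, and stays below 10% at 45%. The exposure is confined to a SelK2 rate close to the margin. This is a cheap improvement of minor priority. It is not a defect in the sample size or the main analysis.

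**What to change.** In Section 5.3, limit the exemption to aspirin of 100 mg or less in stable use before randomization, and state that resuming the same dose after a perioperative pause counts as stable use. Bar new starts and dose increases until venography, unless medically necessary under the exception already in that section. Exclusion 15 needs at most matching wording, since an eligibility criterion cannot bar a start after randomization.

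In Section 10.3.2, add one by-arm table of mITT patients who started or increased aspirin between randomization and venography. Keep mITT as the main analysis, and do not rely on removing these patients from PP as a correction. The conduct rule is the main protection, and the table shows whether it held.

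The cost is a sentence or two in Section 5.3 and one table from dates the eCRF already requires. Sample size does not change. The one practical downside is that a site that would otherwise start aspirin after TKA must wait until venography, about Day 11 ± 2.
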